## Summary

**Background:** In contrast to treatment for chronic heart failure, which is based on several large prospective randomized controlled trials, treatment for acute heart failure is largely based on uncontrolled studies, clinical experience and expert opinion. Perhaps at least in part related to the uncertainties in the treatment of acute heart failure, outcome of patients with acute heart failure is extremely poor. Mortality is 50% at three years. More than 85% of patients with acute heart failure are treated in the non-ICU / CCU setting - the Emergency Department and the regular medical ward. Unfortunately, appropriate treatment is particularly ill-defined in this setting.

**Aim:** to test the hypothesis that a comprehensive approach using an early goal-directed decrement of preload and afterload with a target systolic blood pressure of 90 to 110 mm Hg by aggressive vasodilatation in patients with acute heart failure in the non-ICU setting is safe, and leads to a better clinical and economical outcome.

**Methodology:** This is a prospective, randomized, controlled multicenter study designed to enroll 770 patients presenting with acute heart failure at the emergency departments at the participating study sites. Patients will be randomly assigned 1:1 after stratification for site and B-type natriuretic peptide (BNP, NT-proBNP) levels to an early goal-directed therapy or standard care according to current guidelines. Early goal-directed therapy applies aggressive vasodilatation using sublingual and transdermal nitrates, hydralazine to avoid tolerance to nitrates, and rapid up-titration of angiotensin converting enzyme inhibitors and angiotensin II receptor blockers with a target systolic blood pressure of 90mm Hg to 110 mm Hg. Timing and dosing of diuretics and all other treatments are left to the discretion of the treating physician in both groups. The primary endpoint is death or heart failure readmission within 180 days. Secondary endpoints include the quantitative assessment of dyspnea, need for admission to the intensive care unit, surrogate markers like BNP or NT-proBNP, the digitally recorded third heart sound, renal function, time to discharge, functional status and quality of life, falls, total treatment cost, and cost-effectiveness. Patients will receive extensive clinical and economic follow-up of at least 360 days. Endpoints will be adjudicated by a clinical endpoint committee blinded to group assignment.

**Potential significance:** It is our hypothesis, that a comprehensive approach using an early goal-directed therapy has the potential to more rapidly improve dyspnea, to more rapidly and more extensively reduce heart failure disease severity as quantified by B-type natriuretic peptide levels and most importantly to reduce the occurrence of death and heart failure readmission. Due to the high cost associated with hospitalizations for heart failure, our study has the potential to define a novel treatment strategy that might also significantly reduce the treatment cost associated with acute heart failure.

[figure not shown]

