### **8.2 Statistical Analysis**

The statistical analyses will be performed using the SPSS / PC (version 14.0, SPSS Inc., USA) software package. A statistical significance level (p-value) of 0.05 will be used. All data will be analyzed on an intention-to-treat basis. Comparisons will be made using the t-test, Mann Whitney U-test, Fisher's exact test, survival analysis (Kaplan Meier method), Cox regression analysis and chi-square test as appropriate. All hypothesis testing will be two-tailed. Statistical support will be performed by [name] from the Institute of Social and Preventive Medicine of the University of Basel.

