### **8.3 Power and Sample Size of the Trial**

Based on the data from the BASEL study (31), a hypothesized 20%-decrease of the composite endpoint death or HF re-hospitalization at 180 days, will require 385 patients per treatment arm to obtain, with a probability of 80, a log rank test result that is statistically significant at the 5%-level.

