### **f. Sample size**

Sample size calculation is based on the on the data from the BASEL V study. A hypothesized 20%-decrease of the composite endpoint death or HF re-hospitalization at 180 days, will require 385 patients per treatment arm to obtain, with a probability of 80%, a log rank test result that is statistically significant at the 5%-level. In order to compensate for an expected 1-2% of patients in whom the primary endpoint could not be assessed at 180 days due to loss to follow-up or complete withdrawal of ICF, it was planned to enroll approximately 780 patients.

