#### **3.1. Randomization**

Group assignment was accomplished with the use of a computer-generated randomization scheme in a 1:1 ratio. Randomization will be stratified for enrolling site and the severity of HF as quantified by the BNP level (below or above 1000 ng/l) or NTpro-BNP level (below or above 4000 ng/l). Patients will be randomized to either the early goal directed group or the control group.

---

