**ii. Adjustments for covariates**

The primary analysis will be adjusted for four strong predictors of the composite primary endpoint (death or HF-rehospitalisation within 6 months): age, HF hospitalization in the year before inclusion, systolic blood pressure, and serum creatinine.

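### The baseline natriuretic peptide is required at entry and is the stated measure of HF severity, but the primary Cox model uses it only as a two-level stratum; a continuous term would add a modest amount of power

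*Combined protocol and SAP*

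**What the plan says.** SAP section numbers below follow the SAP's contents list.

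- **Entry.** Protocol 4.1 makes a BNP or NT-proBNP threshold part of the inclusion criteria, with lower thresholds at BMI 35 or above. Patients on LCZ696 may enter on NT-proBNP only.
- **Severity and randomization.** Protocol section 5 and SAP 3.3 stratify by site and by "the severity of HF as quantified by the BNP level (below or above 1000 ng/l", or NT-proBNP below or above 4000 ng/l.
- **Primary model.** SAP 6.1 specifies a Cox model stratified by centre and the randomization factor. SAP 6.6.2 adds: "The primary analysis will be adjusted for four strong predictors of the composite primary endpoint". The four are age, HF hospitalization in the previous year, systolic blood pressure and creatinine. No continuous peptide term appears.
- **Primary test.** SAP 10.1.1 names a log-rank test for significance at 180 days. SAP 6.6.3 confines centre adjustment to sensitivity analyses, which does not agree with SAP 6.1.
- **Stored samples.** Under the general procedures in protocol section 5, a baseline sample is kept, and NT-proBNP is to be measured collectively after discharge.

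The phrase "heart failure disease severity as quantified by B-type natriuretic peptide levels" in the protocol Summary describes a hoped-for effect of treatment. It shows how the sponsor regards the marker but says nothing about the model. The randomization and covariate sections carry this point.

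**The concern.** A two-level stratum treats all patients on one side of the cut as equal in severity. The BNP entry threshold is 500 ng/l (350 at high BMI) and the cut is 1000 ng/l, so the upper stratum has no ceiling: patients at 1,100 and 10,000 ng/l share it. If the peptide predicts death or HF re-hospitalization within strata, leaving that variation out of a Cox model pulls the treatment hazard ratio toward 1 and costs some power. The value should exist for every correctly enrolled patient, so the remedy needs no new data collection.

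**Working it through.** **Inputs from the documents.** Protocol 8.2: "A statistical significance level (p-value) of 0.05 will be used" and "All hypothesis testing will be two-tailed". SAP 3.2: "A hypothesized 20%-decrease of the composite endpoint death or HF re-hospitalization at 180 days", which "will require 385 patients per treatment arm to obtain, with a probability of 80%, a log rank test result". Allocation is 1:1, total 770, with about 780 enrolled to allow for 1-2% loss.

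**Inputs the documents do not give.** Protocol 8.3 says only "Based on the data from the BASEL study", with no control risk. The decrease is not labelled relative or absolute. Nothing states how prognostic the peptide is beyond its stratum and the four covariates.

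**Step 1: reproduce 385 per arm.** Assume a relative reduction, 50% versus 40% at 180 days.

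- Hazard ratio: ln(1 − 0.40)/ln(1 − 0.50) = 0.737.
- Schoenfeld: events = 4(1.96 + 0.842)²/(ln 0.737)², about 338. Divided by the mean risk 0.45 and by two arms, this is 376 per arm.
- Freedman: events = (1.96 + 0.842)² × [(1 + 0.737)/(1 − 0.737)]², about 343, or 382 per arm.
- Two proportions without continuity correction: 388 per arm.

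All are within 3% of 385. Control risks of 45% (455 to 466 per arm) and 55% (311 to 324) do not fit, nor does an absolute 20-point fall (at most about 100). So 50% is back-solved and remains an assumption. The sizing rests on an unadjusted test.

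**Step 2: what the cut discards.** For a normal log peptide split at its median, the two-level version keeps 2/π = 64% of the variance. In the simulation below it kept about 61% with half the patients above the cut, and 43% to 66% with 70% or 25% above it.

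**Step 3: power.** Simulation of 770 patients, 3000 runs per row (Monte Carlo standard error about 0.6 points; both models fitted to the same data). Marginal risks were held near 50% and 40%, with 17 sites of unequal size. The other covariates together were assumed to have SD 0.5 on the log-hazard scale. "Planned" is the Cox model stratified by site and two-level peptide, with the other covariates.

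| Assumed peptide HR per SD | Planned | Plus continuous log peptide | Gain (points) |
|---|---|---|---|
| 1.0 | 84.6% | 84.5% | −0.1 |
| 1.1 | 85.6% | 85.7% | 0.1 |
| 1.2 | 85.5% | 86.0% | 0.5 |
| 1.3 | 86.5% | 87.3% | 0.8 |
| 1.5 | 88.1% | 90.0% | 1.9 |
| 1.75 | 88.0% | 91.0% | 3.0 |

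At HR 1.3, with 25% or 70% of patients above the cut, the gain is 0.6 or 1.1 points.

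**Step 4: as sample size.** Using [(z after + 1.96)/(z before + 1.96)]² − 1, where z is the normal quantile of power:

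- HR 1.2: (3.040/3.018)² − 1, about 1.5% of 770, or 11 patients.
- HR 1.5: (3.242/3.140)² − 1, about 6.6%, or 51 patients.

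These conversions carry the Monte Carlo error of the power figures.

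**Step 5: choice of test.** In the same runs the unadjusted test had about 81% to 83% power, so the planned adjusted model already gains about 3 to 6 points over it. Which test is primary matters more than how the peptide is coded.

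**The case against.** The strongest reply is that nothing here is wrong. The SAP pre-specifies an adjusted model, takes its four covariates from a cited prediction-model paper, includes the peptide as a stratum and examines it as a subgroup. A fifth covariate is a refinement, and its benefit depends on a strength the documents do not give. This largely stands: the analysis is valid as planned, the gain is small over a plausible range, and at HR 1.0 per SD it is nil.

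It is also fair that the term is not quite free. Patients enter on two assays, and standardising within assay equates groups that may differ in severity. The imputation in SAP 6.5 and 10.1.5 is for sensitivity analyses, so a missing covariate in the primary model needs its own rule.

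Two stronger readings are tempting and should not be drawn.

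- **That the trial falls short of 80% power.** Simulated power of about 77% to 79% for the stratified model can be obtained at 49% control risk with hazard ratio 0.739. But 0.739 = ln(1 − 0.392)/ln(1 − 0.49) is the marginal ratio for a 20% reduction. Entered as the conditional ratio beside a score of SD 0.5, it implies a reduction of only 18.5%, 18.1% or 17.6% at peptide HR 1.2, 1.4 or 1.6 per SD. That is a smaller effect than the SAP hypothesises. With marginal risks held at 50% and 40%, no shortfall appears.
- **That the peptide stratum may also be dropped.** SAP 6.6.3 speaks only of centre effects. SAP 6.1 keeps the randomization factor.

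**Conclusion.** The point holds as a low-cost improvement. A severity marker required at entry reaches the primary model only in two levels, and its continuous value is unused. The loss is a forgone bonus of about 0 to 3 power points on a design sized without any adjustment. It is about 0.5 to 2 points if the peptide's hazard ratio per SD, given the other covariates, is 1.2 to 1.5. These figures rest on an assumed 50% control risk, a relative 20% reduction and assumed covariate distributions. If the term adds nothing, the cost is negligible (84.6% versus 84.5%). The benefit reaches the primary p-value only if the adjusted Cox model, not the log-rank test, is the primary test.

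**What to change.** Before database lock:

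1. In SAP 6.6.2 add log baseline natriuretic peptide as a fifth, continuous covariate. Either standardise it within the entry assay and include an assay indicator, or use NT-proBNP from the stored baseline sample, with the entry value as fallback where the sample is missing. A fallback BNP value needs the same standardisation and indicator.
2. Keep the stratification by randomization factor.
3. State that the adjusted, stratified Cox model is the primary test. Reconcile SAP 6.1 and 6.6.2 with the log-rank test in 10.1.1 and the centre statement in 6.6.3.

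The cost is one coefficient against roughly 340 expected events (at the assumed 50% control risk), plus an assay rule and a missing-value rule. No new patients or visits are needed. The adjusted hazard ratio becomes conditional on one more variable, which the report should say.

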## 1. Introduction

**Heart failure (HF)** is a major public health problem especially in industrialized nations. Approximately 15 million Europeans and North Americans have HF and over 1.5 million new cases of HF are diagnosed each year (1,2). Despite advances in diagnosis and treatment, the number of HF admissions has increased steadily, in part due to improved survival rates of patients with acute myocardial infarctions. During the past years, remarkable improvements in outcome of **chronic HF** could be achieved by introducing angiotensin converting enzyme inhibitors (ACE-inhibitors)(3), angiotensin II receptor blockers (ARB) (4,5), beta-blockers (6,7) and spironolactone (8) into the therapeutic strategy, making these agents standard of care and indispensable part of the medication regimen (1).

In contrast to medical therapy for chronic HF, which is scientifically based on several large prospective randomized controlled trials, therapy for **acute HF** is largely based on uncontrolled studies, clinical experience and expert opinion (2). The treatment guidelines of the European Society for Cardiology (ESC) for acute HF recommend the use of supplemental oxygen, morphine, vasodilators, diuretics and mechanical ventilatory support if necessary (2). Perhaps at least in part related to the uncertainties in the treatment of acute HF, outcome of patients with acute HF is extremely poor. Mortality is 50% at three years (9,10) even for patients treated in centers of excellence.

**Figure 1:** After hospitalization for acute HF, patients experience high mortality (9).

Although less than 15% of patients with acute HF are treated in the ICU / CCU setting, recent industry-initiated studies have enrolled predominately ICU / CCU patients and investigated single agents for their ability to impact on clinical outcome (11–15). None of these was able to show clinical benefit to the patient until now.

For multiple reasons including need for restrictive use of the limited number of ICU hospital beds available, the vast majority (more than 85%) of in general elderly patients with acute HF are treated in a **non-ICU setting**. Unfortunately, the optimal treatment of acute HF in the non-ICU setting is particularly ill defined. Uncertainties include the questions which drug to use, when to initiate them, which doses to use, and what pathophysiologic aims to pursue. Pathophysiological considerations and

preliminary data from the ICU setting suggest that aggressive venous and arterial vasodilatation may improve short and long-term outcome. Despite the presence of multiple undisputed differences between the ICU and non-ICU setting, the results of recent ICU studies can be seen as hypothesis generating regarding the optimal treatment in the non-ICU setting.

[figure not shown]
First, there is evidence from a recent ICU study using ultrafiltration for removal of excess fluid in selected patients unresponsive to standard doses of diuretics that improvements in initial in-hospital therapy have the potential to reduce re-hospitalizations and days in hospital during long-term (16). Second, aggressive decrement of preload and afterload in the ICU by intravenous nitrates seems to improve initial outcome (17–19). Cotter et al. compared low vs. high doses of intravenous nitrates in combination with diuretics in acute HF with pulmonary edema. Aggressive vasodilatation was associated with a reduced number of myocardial infarctions, higher oxygen saturation and reduced endotracheal intubations rates (17). Comparable results supporting aggressive vasodilatation in acute HF were achieved by Sharon et al. who compared high-dose intravenous nitrates versus BiPAP (non-invasive) ventilation combined with standard treatment in patients with pulmonary edema due to acute HF. Patients treated by aggressive vasodilatation had lower mortality rates, lower incidence of myocardial infarction and lower requirement for intubation as compared to the patients in the BiPAP group (18).

The transfer of an aggressive treatment strategy from the ICU to the non-ICU setting will require multiple adjustments (20), particularly considering limited patient monitoring, as well as the higher age and increased comorbidity in the non-ICU patients.

**Nitrates** have been used in the treatment of acute HF for several decades. Nitrates are converted to nitric oxide thereby stimulating the production of cyclic guanosine-monophosphate in smooth muscle cells thus promoting relaxation. In the last years, various preparations of organic nitrates have been extensively evaluated for their hemodynamic effect in patients with HF. All available formulations including oral (21), intravenous (19), and transdermal (22) share a similar hemodynamic effect and cause a substantial reduction in right and left ventricular filling pressure, systemic vascular resistance, systemic blood pressure, an increase in cardiac output and little or no change in heart rate (21). Increase in cardiac output is mostly related to the reduction in left ventricular afterload, but also influenced by a decrease in pulmonary vascular resistance (11), improvement in myocardial ischemia and reduction in the degree of mitral regurgitation (21). These acute hemodynamic effects make organic nitrates suitable for the treatment of acute HF in the setting of acute myocardial infarction or worsening of chronic HF(21).

Already in 1985, the dose requirements of transdermal nitroglycerin to achieve a significant and consistent drop in left ventricular filling pressure has been defined (23). According to these invasive hemodynamic studies, 60 mg / 24h of Nitroderm TTS are necessary to obtain a drop of 30% in left ventricular filling pressure in the majority of patients with HF. For unknown reasons, clinical practice has ignored this finding and used doses of 5 mg to 10 mg / 24 h Nitroderm TTS in the setting of acute HF.

Continuous administration or frequent dosing of nitrates may lead to early development of nitrate tolerance, associated with significant attenuation of nitrate-mediated hemodynamic effects (21,22). Hemodynamic and clinical studies have suggested that nitrate tolerance can be avoided and both, hemodynamic and clinical response improved if nitrates are used in combination with hydralazine.

[figure not shown]
**Figure 2:** Effects of 24 h of nitroglycerin infusion alone (NTG) or in combination with hydralazine (NTG + HYD) on mean pulmonary capillary wedge pressure (21).

**Hydralazine** is a peroral applicable vasodilator with direct relaxant effect on arteriolar smooth muscle, which also has anti-oxidative effects. Several studies could show that the concomitant use of nitrates and hydralazine in patients with HF prevents development of nitrate tolerance and results in a persistent nitrate-mediated hemodynamic effect (21–24). The initial rationale for use of organic nitrates in combination with hydralazine was their complementary “nitroprusside-like” hemodynamic effect caused by the predominant venodilatory action of organic nitrates and the arterial-dilatory effect of hydralazine. This combination leads to a significant improvement in cardiac function, with a concomitant reduction in right and left ventricular filling pressures and augmentation of cardiac output (21). Based on this hemodynamic profile, the Vasodilator Heart Failure Trial (V-HeFT) compared the effect of nitrates in combination with hydralazine vs. placebo on outcome of patients with chronic HF and demonstrates improvements in left ventricular ejection fraction (LVEF), exercise tolerance, and survival in patients treated with isosorbide dinitrate (ISDN) and hydralazine (25). The V-HeFT II study compared the effects of ISDN and hydralazine versus the ACE-inhibitor enalapril and could demonstrate a significant improvement in LVEF during treatment with ISDN and hydralazine (26). A retrospective analysis of V-HeFT I and V-HeFT II showed that the benefit of ISDN and hydralazine was seen predominately in African Americans. This observation led to the design of the African American Heart Failure Trial (A-HeFT), which confirmed the survival benefit of these drugs in combination vs. placebo in African American patients with chronic HF(27).

It is currently unknown whether a strategy of cautiously unloading the heart and slowly increasing the dose of disease modifying therapy with ACE-inhibitors - the standard of care in the non ICU setting - is superior, equal, or inferior to an early goal directed therapy that targets a rapid and maximal reduction in the severity of HF (as

theoretically quantifiable by B-type natriuretic peptide or pulmonary capillary wedge pressure values; Figure 3) using aggressive vasodilatation.

Recent evidence from pilot studies for a long-term benefit of early aggressive therapeutic intervention in acute HF and the promising results obtained by vasodilatation with nitrates and hydralazine in chronic HF provide the rationale for our hypothesis that an early goal-directed decrement of preload and afterload with a target systolic blood pressure of 90 mm Hg to 110 mm Hg by aggressive vasodilatation in patients with acute HF in the non-ICU setting is safe, and leads to a better clinical and economical outcome. The early goal directed therapy as implemented by our protocol is expected to result in a more rapid resolution of symptoms, reduced time to discharge and reduced disease severity at the time of discharge. In addition, patients in the intervention group will receive a significantly higher dose of disease-modifying drugs like ACE-inhibitors and ARBs at the time of discharge. The difference in the dose of ACE-inhibitors and ARBs between both groups is expected to prevail within the first months of follow-up. The combination of both, improved disease state at discharge and higher doses of disease-modifying drugs during most of the study period is expected to result in a significant improvement in patient morbidity and mortality (11,28). This project is well in line with our previous research in this setting (10,29–31).

**Figure 3:** Theoretical model of expected effects of two different treatment strategies on quantitative markers of HF (B-type natriuretic peptide (BNP) or pulmonary capillary wedge pressure (PCWP)). Due to the aggressive preload and afterload decrement especially during the first 48 h of early goal directed treatment therapy, B-type natriuretic peptide and pulmonary capillary wedge pressure are expected to decrease faster and more pronounced than in the standard of care group.

